**TABLE 3: Lenalidomide Dose Modification Steps**

Current Lenalidomide Dose	One Level Dose Reduction
25 mg daily on Days 1-21 every 28 days	20 mg daily on Days 1-21 every 28 days
20 mg daily on Days 1-21 every 28 days	15 mg daily on Days 1-21 every 28 days
15 mg daily on Days 1-21 every 28 days	10 mg daily on Days 1-21 every 28 days
10 mg daily on Days 1-21 every 28 days	5 mg daily on Days 1-21 every 28 days*
5 mg daily on Days 1-21 every 28 days*	See above

**TABLE 4: Romidepsin Dose Modification Steps**

Current Romidepsin Dose	One Level Dose Reduction
14 mg/m  daily on Days 1,8,15	10 mg/m  daily on Days 1,8,15
10 mg/m  daily on Days 1,8,15	8 mg/m  daily on Days 1,8,15
8 mg/m  daily on Days 1,8,15	8 mg/m  daily on Days 1,15

**TABLE 5: Dose Modifications for Lenalidomide and Romidepsin**

NCI CTC Toxicity Grade	Dose Modification Instructions (also see Instructions for Initiation of a New Cycle above)
Grade 3 neutropenia not associated with fever	
 
• Hold lenalidomide and romidepsin dose.
 
• Follow CBC at least weekly.
 
• Upon recovery to grade <math>\leq</math> 2 resume romidepsin and lenalidomide at one dose reduction.
 
• Omitted doses are not made up (Romidepsin doses may be given up to 3 days late).
 

Grade 3 neutropenia associated with fever (temperature <math>\geq 38.5^{\circ}</math> C) or Grade 4 neutropenia	
 
• Hold lenalidomide and romidepsin dose.
 
• Follow CBC at least weekly.
 
• Upon recovery to <math>\leq</math> grade 2 resume lenalidomide and romidepsin at next lower dose level.
 
• Omitted doses are not made up. (Romidepsin doses may be given up to 3 days late)
 

Thrombocytopenia <math>\geq</math>Grade 3 (platelet count <math>< 50,000/\text{mm}^3</math>)	
 
• Hold lenalidomide and romidepsin dose.
 
• Follow CBC at least weekly.
 
• Upon recovery to <math>\leq</math> grade 2 resume lenalidomide and romidepsin at next lower dose level.
 
• Omitted doses are not made up. (Romidepsin doses may be given up to 3 days late)
 

Non-blistering rash	
Grade 3	
 
• If Grade 3, hold lenalidomide dose. Follow at least weekly.
 
• If the toxicity resolves to grade 1, resume lenalidomide at next lower dose level.
 
• Omitted doses are not made up.
 

Grade 4	
 
• If Grade 4, discontinue lenalidomide. Remove patient from study.
 

Desquamating (blistering) rash- any Grade	
 
• Discontinue lenalidomide. Remove patient from study.
 

Neuropathy	
Grade 3	
 
• If Grade 3, hold lenalidomide dose. Follow at least weekly.
 
• If the toxicity resolves to grade 1 resume lenalidomide at next lower dose level.
 
• Omitted doses are not made up.
 

Grade 4	
 
• If Grade 4, discontinue lenalidomide. Remove patient from study.
 

Venous thrombosis/embolism <math>\geq</math> Grade 3	
 
• Hold lenalidomide and romidepsin. Start therapeutic anticoagulation, if appropriate.
 
• Restart lenalidomide and romidepsin at investigator's discretion after discussion with PI (reduce 1 dose level of each drug).
 
• See Anticoagulation Consideration
 

TABLE 5: Dose Modifications for Lenalidomide and Romidepsin	
NCI CTC Toxicity Grade	Dose Modification Instructions (also see Instructions for Initiation of a New Cycle above)
Hyperthyroidism or hypothyroidism	

• Omit lenalidomide for remainder of cycle, evaluate etiology, and initiate appropriate therapy.

• See Instructions for Initiation of a new cycle and reduce the dose of lenalidomide by 1 dose level.

Other non-hematologic toxicity <math>\geq</math> Grade 3	

• Hold lenalidomide and romidepsin dose. Follow at least weekly.

• If the toxicity resolves to <math>\leq</math> grade 2 resume lenalidomide and romidepsin at one dose reduction.

• Omitted doses are not made up.(Romidepsin doses may be given up to 3 days late)

• If no further dose reduction levels patient will be removed from study.

### **9.7.2 Romidepsin Dose Modification in Case of Cardiac Toxicity**

The guidelines for cardiac monitoring and timing of ECG assessments are presented in Table 6. Prolongation of QTc  $\geq$ 500 msec is considered to be an alert associated with romidepsin administration.

**Table 6: Dose alteration based on cardiac abnormalities**

Parameter/Symptoms	Change	Action	Dosing/ Continuation
Sinus tachycardia	Pulse >140/min after recumbency		
Atrial dysrhythmia (SVT, atrial fibrillation, or atrial flutter)	New occurrence		
Prolongation of QTc compared to post anti- emetic ECG	To $\geq$ 500 msec unless BBB or pacemaker present; see section10.4	Hold further dosing and treat appropriately. If desired, the principal investigator or a local cardiologist may be consulted.	If resolved, restart romidepsin at reduced dose as per table 4. If not resolved, take off study.
Heart rate	> 120 bpm with > 20 bpm increase from previous evaluation;		
Ventricular tachycardia	$\geq$ 3 beats in a row		
Ventricular fibrillation; Torsade de Pointes	New occurrence	Hold further dosing and treat appropriately. The medical monitor should be notified immediately and local cardiologist should be consulted.	Hold further dosing until medical monitor and cardiologist evaluation is complete
A subsequent episode of any of the above, despite dose reduction		Take off study	
T-wave morphology	Inversion of $\geq$ 4 mm a	Hold further dosing and treat appropriately. If desired, the medical monitor or a local cardiologist may be consulted.	If resolved, restart romidepsin at reduced dose. In some patients, ST segment and T- wave morphology changes may recur despite a dose reduction to 10mg/m  . In such cases, further treatment should be held until the ECG changes resolve. If the patient experiences no concomitant clinical events, treatment may be resumed at the reduced dose of 10 mg/m  If not resolved, take off study
ST-segment	Depression of $\geq$ 2 mm b		

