## 10.4 Cardiac Alert Findings (post anti-emetic)

In the event of an alert finding, the individual decision about a delay of administration, dose reduction, or withdrawal from the study will be made by the Investigator (in association with local cardiologist, if preferred). All alerts must be confirmed via manual read of the patient's ECG; the machine reading alone is not adequate. The following findings are considered to be cause for alert and if they occur, should be reported as AEs or SAEs, as appropriate:

- QTc (Bezett's—by machine read) is  $\geq 500$  msec

- QTc (Friderica's) will be used for manual reads by either the physician or cardiologist.
- If the patient has a known bundle branch block (BBB) and a baseline QTc of >470 msec a change in QTc of > 30 msec from the post antiemetic ECG will be used as criteria for an adverse event (as opposed to absolute QTc) and would be graded as a grade 3 adverse event. If no change >30 msec has been documented after completion of cycle 4 no further ECG will be required.
- If the patient has a pacemaker and a baseline QTc of >470 msec a change in QTc of >30 msec from the post antiemetic ECG in either the native rhythm or a paced rhythm will be used as criteria for an adverse event and would be graded as a grade 3 adverse event. A change can only be assessed if the rhythm is conserved (i.e. native to native rhythm). If a conversion of rhythm is seen (i.e. native to paced), and if the patient is asymptomatic no adverse event will be noted. If symptomatic it would be graded as a grade 3 adverse event. If no change >30 msec has been documented after completion of cycle 4 no further ECG will be required.
- Ventricular arrhythmia: VT ( $\geq 3$  beats in a row) or VF.
- Sinus tachycardia (pulse  $>140$ /min after recumbency).
- Heart rate is  $\geq 120$  bpm with  $\geq 20$  bpm increase from previous evaluation.
- New occurrence of atrial dysrhythmias (SVT, atrial fibrillation, or atrial flutter).
- Abnormal ST and/or T-wave changes including ST depression of  $\geq 2$  mm (as measured from isoelectric line to the ST segment at a point 60 msec at the end of the QRS complex); T-wave inversion of  $\geq 4$  mm (measured from isoelectric line to peak of T-wave) as long as the main QRS vector is positive.
- Ventricular tachycardia, including Torsade de Pointes.

See Table 6 in Section 9 for recommended dose reductions, etc., in the above situations.

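### Table 6 exempts every patient with bundle branch block or a pacemaker from the QTc ≥500 msec hold, but Section 10.4 supplies a substitute criterion only when baseline QTc exceeds 470 msec

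*Combined protocol and SAP*

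**What the plan says.** All references are to the combined protocol and SAP.

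- **Section 9.7.2, text.** A QTc of at least "500 msec is considered to be an alert associated with romidepsin administration". No exception is made for BBB or a pacemaker.
- **Table 6, QTc row.** The row is labelled "Prolongation of QTc compared to post anti- emetic ECG". The trigger is a QTc of 500 msec or more, "unless BBB or pacemaker present; see section10.4". The action is to hold dosing, then: "If resolved, restart romidepsin at reduced dose as per table 4". If the finding does not resolve, the patient comes off study.
- **Section 10.4.** A QTc of 500 msec or more is listed as an alert. For any alert, "the individual decision about a delay of administration, dose reduction, or withdrawal from the study will be made by the Investigator". Two bullets then set a different criterion. One begins "If the patient has a known bundle branch block (BBB) and a baseline QTc of >470 msec", the other "If the patient has a pacemaker and a baseline QTc of >470 msec". In these patients a change of more than 30 msec counts instead and is grade 3; for BBB it is measured "from the post antiemetic ECG will be used as criteria for an adverse event (as opposed to absolute QTc"). The section closes by sending the reader to Table 6 for recommended dose reductions.
- **Section 10.5.** A QTc of 500 msec or more is to be repeated twice. If the mean is still at that level, the reader is sent to Table 6.

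**The concern.** The exemption and its replacement cover different groups. Table 6 lifts the absolute criterion for all patients with BBB or a pacemaker. Section 10.4 replaces it only for those with baseline QTc above 470 msec. Patients at or below 470 msec fall between the two.

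What is at stake is individual patient safety and consistency between sites. The protocol treats QTc prolongation as a leading romidepsin risk: it sets entry limits, bans QTc-prolonging drugs, requires electrolyte correction and schedules ECGs around infusions. Two sites that both follow the text could dose the same patient differently after the same ECG.

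**Working it through.** There is no plan figure to reproduce. The check sets the rules side by side.

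**1. Who is covered.** Exempt under Table 6: BBB or pacemaker. Substitute under Section 10.4: BBB or pacemaker, and baseline above 470 msec. Exempt without a substitute: BBB or pacemaker, and baseline of 470 msec or less.

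| Patient | Table 6 trigger (≥500 msec) | Section 10.4 criterion (>30 msec) |
|---|---|---|
| No BBB or pacemaker | applies | not relevant |
| BBB or pacemaker, baseline >470 | lifted | applies, grade 3 |
| BBB or pacemaker, baseline ≤470 | lifted | does not apply |

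**2. Can these patients enroll?** Yes. Section 6.2 excludes a QTc of 480 msec or more and does not list BBB or a pacemaker as an exclusion. The discussion with the principal investigator is required only at 480-499 msec in phase IIa, so it does not reach patients at 470 or below.

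**3. Example.** A lymphoma patient on 14 mg/m² (Section 9.3) has baseline 465 and a confirmed 510 msec.
- 510 ≥ 500, so without BBB the Table 6 row applies: hold, then 10 mg/m² if resolved (Table 4), off study if not.
- With BBB the Table 6 trigger is lifted. Since 465 ≤ 470, the Section 10.4 substitute does not apply either. If the post-antiemetic ECG was also 465 (an assumption), the rise is 510 − 465 = 45 msec, above 30, but as written that criterion is not open to this patient.

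**4. Following the references.** Table 6 points to Section 10.4. Sections 10.4 and 10.5 point back to Table 6. For baseline ≤470 the chain ends at the exempting cell.

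**5. What remains for that patient.**
- The alert, its manual confirmation and the two repeat ECGs, with the dosing decision left to the investigator.
- Section 10.1 (new cycle) and Section 10.2 (each later dose), which require clinically significant toxicity to have come down to grade 2 or less. These act only if the event is judged clinically significant and above grade 2.
- Possibly the Table 5 row for other non-hematologic toxicity of grade 3 or more. Section 9.7.3 keeps toxicities already dealt with out of Table 5, and QTc prolongation is one of them, so this is doubtful. That row would also reduce lenalidomide, which Table 6 does not.

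**6. Secondary: when ECGs may stop, baseline >470.** Section 10.4 requires none after cycle 4 if no change above 30 msec was seen. Section 10.5 allows stopping after cycle 2 if no QTc exceeded 480 msec, and later only after two consecutive cycles at or below 480.
- Stable at 471-480: Section 10.5 allows a stop after cycle 2, Section 10.4 after cycle 4. Both are permissive, so going on to cycle 4 breaches neither.
- Stable at 481-499: Section 10.4 allows a stop after cycle 4; Section 10.5 gives no point at which to stop.

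Footnote 2 of Table 7 names only Section 10.5 for the ECG schedule, and no order of precedence is stated.

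**The case against.** The strongest reply is that the Table 6 cell should be read with its own pointer. On that reading the exception is the one Section 10.4 defines. Absolute QTc gives way only above 470 msec, and at or below 470 the 500 msec criterion stays. This is a reasonable inference and may well be the intent. It does not settle the matter, because the cell itself has no such limit and Section 10.4 refers the dosing question back to it.

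Three stronger readings are tempting, and the documents do not support them.

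- *These patients are unprotected while others have a mandatory hold.* Section 10.4 leaves the decision on every alert to the investigator, with or without BBB, and calls the Table 6 reductions recommended. The alert and the Section 10.1 and 10.2 checks also remain.
- *A change above 30 msec has no dosing consequence when baseline exceeds 470.* The Table 6 row uses the same post-antiemetic comparator and points to Section 10.4, so the criterion is arguably imported with the row's action. If it is not, the Table 5 row for grade 3 or more arguably catches it.
- *The ECG stop rules flatly contradict each other.* Section 10.4 can be read as the specific rule and Section 10.5 as the general one. A patient stable at 481-499 could never meet the general rule, which is an evident reason for a special one. Section 10.5 also lets investigators do more ECGs.

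**Conclusion.** The gap in the Table 6 cell is real on a literal reading. Patients with BBB or a pacemaker and baseline QTc of 470 msec or less lose the specified QTc action and receive no substitute. What they keep is an alert with investigator discretion and the general toxicity checks. The conclusion rests on the wording of the cell; the narrower reading through the pointer is open to a careful reader but is not stated.

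The documents give no number of affected patients, and it is probably small. A reader might infer that the gap distorts the dose-limiting toxicity (DLT) count. Section 4.1 defines non-hematologic DLTs by grade and attribution, not by whether a Table 6 hold applied. A QTc hold could enter only through a drug-related delay of a week or more in starting cycle 2, and no size for that can be derived. No sample size or operating characteristic changes.

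The ECG stop rules are a minor point of cross-referencing and do not carry this conclusion.

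**What to change.** **Main change, one cell.** Reword the Table 6 QTc trigger to: *To ≥500 msec, unless BBB or pacemaker is present and baseline QTc is >470 msec; in those patients, increase of >30 msec from the post antiemetic ECG (pacemaker: conserved rhythm, see Section 10.4).* Keep the row's existing action. Patients at or below 470 msec then keep the 500 msec criterion, and the 30 msec criterion has an explicit dosing action. The cost is the wording and an occasional extra hold.

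**Secondary, optional.** Add a sentence to Section 10.5, and a reference in footnote 2 of Table 7, saying how the Section 10.4 cycle-4 rule relates to Section 10.5 when baseline exceeds 470 msec. This involves a trade-off: giving Section 10.4 precedence at 481-499 msec would let patients with the longest baseline QTc stop ECGs where Section 10.5 would continue them. The investigators and cardiologist should choose which rule governs there.

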**NOTE: Cardiac findings that require dose modification should be reported as AEs or SAEs as appropriate.**

a Measured from isoelectric line to peak of T-wave.

b Measured from isoelectric line to ST segment.

### **9.7.3 Other Non-Hematologic and Hematologic Toxicities**

All previously established or new toxicities observed any time, with the exception of those mentioned above, are to be managed as summarized in Table 5.

- Dose interruption or study discontinuation is not required for lymphopenia of any grade.
- Dose reductions should not be performed for alopecia or for non-infectious diarrhea, nausea, or vomiting that has not been treated with aggressive anti-diarrheal or anti-emetic support.

### **9.8 Treatment Adherence**

Research personnel will review the dosing instructions with patients. Patients will be provided with a medication diary and asked to record the drug administration. Patients will be asked to bring any unused drug and empty drug containers to the research personnel at the beginning of each cycle. Research personnel will count and record the number of used and unused drug at the beginning of each cycle and reconcile with the patient diary.

Any unused Revlimid® (lenalidomide) should be returned to the patient for disposition in accordance with the REMS® program.

### **9.9 Concomitant Therapy**

#### **9.9.1 Recommended Concomitant Therapy**

Subjects will receive full supportive care, including transfusions of blood and blood products, electrolyte supplementation, antibiotics, analgesics, and antiemetics when appropriate.

#### **9.9.2 Anticoagulation Consideration**

Lenalidomide increases the risk of thrombotic events in patients who are at high risk or with a history a thrombosis, in particular when combined with other drugs known to cause thrombosis. When lenalidomide was combined with other agents such as steroids (e.g. dexamethasone, prednisone), anthracyclines (Doxil, Adriamycin) and erythropoietin the risk of thrombosis is increased. For information on the risk of venous thromboembolism with combined oral contraception see Appendix C: Risks of Fetal Exposure, Pregnancy Testing Guidelines and Acceptable Birth Control Methods.

Consideration should be given to the optional use of aspirin (81 or 325 mg) or some other form of prophylaxis as deemed appropriate. Low molecular weight heparin may be utilized in patients that are intolerant to ASA. Coumadin should be

used with caution and close monitoring of INR. Carefully monitor prothrombin time (PT) and International Normalized Ratio (INR) in patients concurrently administered ISTODAX® and Coumadin derivatives.

If prophylactic anti-coagulation is used, it will be held for platelet counts < 50,000, and then restarted when platelet counts are above this level.

## **10.0 EVALUATION DURING TREATMENT/INTERVENTION**

### **10.1 A new cycle of treatment may begin on the scheduled Day 1 of a new cycle if:**

- ANC is  $\geq 1.0$  K/ $\mu$ L
- Platelet count is  $\geq 70$  K/ $\mu$ L or within 10 K/ $\mu$ L of baseline.
- Serum creatinine concentration  $\leq 2.0 \times$  ULN or  $\leq$  baseline
- AST (SGOT) and ALT (SGPT)  $\leq 2.0 \times$  ULN or  $\leq 3.0 \times$  ULN in presence of demonstrable liver metastases.
- Serum potassium and magnesium are within normal range.
  - In cycle 2 and beyond in Phase Ib and any cycle in Phase IIa, magnesium and potassium levels may be checked up to 3 days prior to administration of romidepsin. If levels are within range at that time point romidepsin may be administered without recheck unless clinically indicated (such as vomiting, diarrhea, or initiation of medications that may affect electrolytes).
  - Supplements must be given to patients whose potassium and/or magnesium are below normal range.
    - Magnesium supplementation: If levels are below normal range, but  $\geq 1.2$  mg/dL, patients can receive at least 2gm magnesium IV and proceed to treatment without re-checking labs. Patients can be treated if magnesium levels are above normal range.
    - Potassium supplementation: If levels are below normal range, but  $\geq 3.2$  mEq/L, patients can receive at least 20mEq potassium IV and proceed to treatment without re-checking labs.
- Any drug-related maculo-papular rash or neuropathy that may have occurred has resolved to  $\leq$  grade 1 severity
- Any other clinically significant adverse events that may have occurred have resolved to  $\leq$  grade 2 severity.

**If these conditions are not met on Day 1 of a new cycle, the subject will be evaluated weekly and a new cycle of treatment will not be initiated until the toxicity has resolved as described above.**

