## **6.0 CRITERIA FOR SUBJECT ELIGIBILITY.**

### **6.1 Subject Inclusion Criteria**

1. Pathology confirmed lymphoma or multiple myeloma.
  - Hodgkin lymphoma is eligible for either phase and will be considered a B-cell lymphoma in the phase IIa study.
  - Phase IIa portion, subjects must have B-cell lymphoma, T-cell lymphoma, or multiple myeloma.
2. Relapse or progression after at least 1 systemic therapy.
3. Measurable disease for phase IIa portion only.

- Lymphoma (includes CTCL patients who are NED in skin): CT or PET/CT by modified Cheson criteria with incorporation of PET.
  - Multiple myeloma: Patient must have measurable disease and therefore must have at least one of the following:
    - i. Serum M-protein  $\geq 0.5\text{gm/dL}$  ( $\geq 5\text{gm/L}$ )
    - ii. Urine M-protein  $\geq 200\text{mg/24hr}$
    - iii. Serum FLC assay: involved FLC  $\geq 10\text{mg/dL}$  ( $\geq 100\text{mg/L}$ ) provided serum FLC ratio is abnormal.
  - CTCL: mSWAT  $>0$ , or absolute Sezary count  $\geq 1000\text{ cells}/\mu\text{L}$ .
4. Age  $\geq 18$  years at the time of signing the informed consent form.
  5. Able to adhere to the study visit schedule and other protocol requirements.
  6. Previous systemic anti-cancer therapy must have been discontinued at least 3 weeks prior to treatment in this study. If there is progression of disease on that therapy and all adverse effects have resolved to Grade 1 or baseline, in which case 2 weeks is acceptable.
  7. Previous radiation, hormonal therapy, and surgery must have been discontinued or completed at least 2 weeks prior to treatment in this study and adverse effects must have resolved. Lymph node or other diagnostic biopsy within 2 weeks is not considered exclusionary.
  8. Short course systemic corticosteroids for disease control, improvement of performance status or non-cancer indication (< 7 days) must have been discontinued at least 7 days prior to study treatment. Stable ongoing corticosteroid use ( $\geq 30$  days) up to an equivalent dose of 15 mg of prednisone is permissible.
  9. ECOG performance status of  $\leq 2$  at study entry (see Appendix A).
10. Laboratory test results within these ranges:
- Absolute neutrophil count  $\geq 1.0/\text{mm}^3$ .
  - Platelet count  $\geq 70\text{ K}/\mu\text{L}$ , if thrombocytopenia is due to bone marrow involvement platelet count must be  $\geq 50\text{ K}/\mu\text{L}$ .

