### **9.7.1 Instructions for Dose Modifications or Interruption During a Cycle**

Dose delay and dose reduction rules for lenalidomide and romidepsin are as follows and summarized in the tables 3, 4, & 5:

- In the event of dose reduction due to hematologic toxicity attributed to study drugs, lenalidomide and romidepsin will be reduced as per Tables 3 & 4.
- In the event of dose reduction due to non-hematologic toxicity attributed to study drugs, lenalidomide and romidepsin will be reduced one level per Tables 3 & 4.
- Missed doses of lenalidomide and/or romidepsin are not made up.
- Interruptions of therapy, including delays in starting a new cycle, of greater than 28 days will result in removal from study.
- Patients remaining on treatment after cycle 6, at the discretion of their physician, may elect to receive romidepsin on a day 1 and 15 schedule each cycle.
  - Patients remaining on treatment after cycle 9, at the discretion of their physician may elect to receive romidepsin on day 1 of each cycle (q4 week dosing) after discussion with the MSK Principal Investigator.
- If a patient is at the lowest dose level and deriving benefit from therapy, they may continue on protocol therapy despite  $\geq$  grade 3 hematologic toxicity or non-clinically significant non-hematologic toxicity after discussion with the MSK principal investigator.

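### Section 10.1 lets a marrow-involved patient with a baseline of 50–59 K/µL start a cycle at 40–49 K/µL, below the 50 K/µL needed to continue one

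*Combined protocol and SAP*

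**What the plan says.** - **Entry.** Section 6.1, item 10, asks for platelets of at least 70 K/µL, with a lower limit for one group: "if thrombocytopenia is due to bone marrow involvement platelet count must be" at least 50 K/µL.
- **Day 1 of a new cycle.** Section 10.1 asks for at least 70 K/µL "or within 10 K/ $\mu$ L of baseline". No absolute count is attached to the baseline route.
- **During a cycle.** Table 5, under Section 9.7.1, holds both drugs for thrombocytopenia of grade 3 or worse, which its row label equates with a count below 50,000/mm³. On recovery to grade 2 or better, sites are to "resume lenalidomide and romidepsin at next lower dose level".
- **Day 8 and Day 15.** Section 10.2 requires at least 50 K/µL before every romidepsin dose except Day 1, with no baseline alternative.
- **Which rule covers Day 1.** Table 5's header tells the reader to "also see Instructions for Initiation of a New Cycle above", and its thyroid row says "See Instructions for Initiation of a new cycle and reduce the dose of lenalidomide by 1 dose level". The new-cycle criteria actually come later, in Section 10.1.
- **Exception.** Section 9.7.1 states: "If a patient is at the lowest dose level and deriving benefit from therapy, they may continue on protocol therapy despite" hematologic toxicity of grade 3 or worse, after discussion with the MSK principal investigator.
- **Time limit.** Section 9.7.1 also states: "Interruptions of therapy, including delays in starting a new cycle, of greater than 28 days will result in removal from study".
- **Anticoagulation.** If prophylaxis is used, Section 9.9.2 says "it will be held for platelet counts < 50,000".

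**The concern.** Rules for starting a cycle are normally at least as strict as rules for continuing one. The protocol follows that order elsewhere: the standard platelet limit is 70 K/µL to start and 50 K/µL to continue, and the neutrophil limit is the same (1.0 K/µL) in Sections 10.1 and 10.2. The baseline clause reverses the order for patients who enter with a marrow-related count in the fifties.

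Such a patient can receive Day 1 romidepsin and begin daily lenalidomide at a count at which Table 5 stops both drugs. Sections 11.1 and 11.2 list thrombocytopenia as a likely effect of each drug. What is at stake is patient safety and a coherent dosing rule in a small group.

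**Working it through.** No figure in the plan needs reproducing. The check compares thresholds, in whole thousands per µL (1 mm³ = 1 µL, so Table 5's 50,000/mm³ is 50 K/µL).

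**Inputs**
- Lowest marrow-related entry count: 50 K/µL (Section 6.1).
- Day 1 limit: 70 K/µL, or baseline minus 10 (Section 10.1).
- Limit to continue: 50 K/µL (Table 5; Section 10.2).

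**Formulas**, with b for baseline
- Lowest Day 1 count now = min(70, b − 10).
- Conflict if b − 10 < 50, that is, if b < 60. Because entry needs b ≥ 50, only b = 50–59 is caught.
- Width of the conflict band = 50 − (b − 10) = 60 − b.
- With a 50 K/µL minimum added, lowest Day 1 count = max(50, min(70, b − 10)).
- For b from 50 to 60, the allowance below baseline then becomes b − 50.

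| Baseline (K/µL) | Lowest Day 1 count now | Conflict band | Lowest Day 1 count with 50 K minimum | Allowance below baseline with minimum |
|---|---|---|---|---|
| 50 | 40 | 40–49 (10 K) | 50 | 0 |
| 55 | 45 | 45–49 (5 K) | 50 | 5 |
| 59 | 49 | 49 (1 K) | 50 | 9 |
| 60 | 50 | none | 50 | 10 |
| 70 | 60 | none | 60 | 10 |

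Counts of 40–49 K/µL lie below Table 5's hold limit and above the 25 K/µL that Section 4.1 uses for grade 4, so they are grade 3 under the protocol's own limits.

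**Could another clause already supply the minimum?**
- Section 10.1's last bullet requires clinically significant events to have settled to grade 2 or better, but it concerns *other* events. Platelets have their own bullet, and a marrow-related low count need not be an adverse event.
- The Section 9.7.1 exception covers only benefiting patients at the lowest dose level, after discussion. It does not explain a rule that applies at every dose level.

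**Waiting time.** Section 10.1 prescribes weekly evaluation. Within 28 days that gives 28/7 = 4 re-checks, at days 7, 14, 21 and 28.

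**The case against.** The strongest reply is that the documents give Day 1 to Section 10.1 alone. Section 10.2 excludes Day 1, Section 9.7.1 is headed as applying during a cycle, Table 5 refers to the new-cycle instructions, and the introduction to Section 9.7 lists starting a cycle and modifying doses within one as separate topics. That reading is right, and it rules out several stronger inferences:

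- *Sites will treat the same Day 1 count differently.* This needs a site to apply a within-cycle table to Day 1, against the headings and cross-references.
- *A patient held late in one cycle can restart without recovering.* Section 10.1 is permissive, and nothing in it cancels a hold already in force under Table 5.
- *DLT counts or the MTD are distorted.* Section 4.1 counts a drug-related wait of a week or more at cycle 2 Day 1 as a DLT, but the delay must be attributed to study drug in a patient whose baseline is disease-related. That is an uncommon possibility. Section 9.3 records the lymphoma MTD as already set.
- *Much of the planned dose will be lost.* The documents do not give the course of platelet counts within a cycle, so no loss can be estimated.
- *There is no limit at all.* None is written, but if baseline means the qualifying count, the entry minimum implies 40 K/µL.

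The clause may also be deliberate. Section 10.1 uses baseline for creatinine and relaxes the liver limits for liver metastases, and Section 9.9.1 provides transfusion support. Section 9.7.1 ties hematologic dose reduction to toxicity attributed to study drugs, although Table 5's platelet hold carries no such wording. This makes the allowance a defensible clinical choice. It does not explain why the allowance ends once the cycle starts: Table 5 and Section 10.2 stop treatment at the counts Section 10.1 accepts.

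**Conclusion.** The point stands as a minor safety and consistency correction. With Section 10.1 as the sole Day 1 rule, patients with marrow-related baselines of 50–59 K/µL may start both drugs at 40–49 K/µL and are then subject to a 50 K/µL limit for continuing. The mismatch is at most 10 K/µL and disappears at a baseline of 60 K/µL.

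This assumes that baseline is the count that qualified the patient. The documents do not define it for this rule, and a lower pre-dose value used as baseline would lower the limit further. The number of patients entering at 50–59 K/µL is not given, and none is assumed.

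**What to change.** 1. Reword the Section 10.1 bullet: *platelets ≥ 70 K/µL, or within 10 K/µL of baseline and ≥ 50 K/µL, except as allowed in 9.7.1 for benefiting patients at the lowest dose level.*
2. Change the Table 5 header to refer to Section 10.1 as the rule for Day 1 of a new cycle.

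The 50 K/µL limit is already used for marrow-involved entry, in Table 5, in Section 10.2 and for holding anticoagulation. No tests are added, since Table 7 already schedules hematology on Days 1, 8 and 15.

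The cost falls on the patients whom the clause serves. A patient with baseline 50 K/µL has no allowance below baseline and must wait for 50 K/µL, with removal if the interruption exceeds 28 days. A drug-related wait of a week or more at cycle 2 Day 1 would count as a DLT. Most of the cost already arises under Table 5, which would hold these patients once the cycle began. What they newly lose is the Day 1 romidepsin dose and any lenalidomide taken before that hold. Baselines of 60 K/µL or more are unaffected.

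If the sponsor intends the allowance, copying it into Section 10.2 and Table 5 would also be consistent. It would permit dosing throughout a cycle at 40–49 K/µL, so the minimum is preferred.
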